present a viable option to safely enhance therapeutic outcomes and expedited treatment gains for exposure-based therapies. D-cycloserine is a partial glutamatergic NMDA receptor agonist that is approved by the United States Food and Drug Administration to treat tuberculosis in high doses, but works as a cognitive enhancer for psychosocial interventions in much lower doses (e.g., 50 mg). DCS has been found to enhance extinction (Walker, Ressler, Lu, & Davis, 2002) and associative learning (Quermain, Mower, Rafferty, Herting, & Lanthorn, 1994) across numerous animal and human studies (Davis, 2011; Fitzgerald, Seemann, & Maren, 2014).

Exposure-based psychosocial interventions that utilize these mechanisms have demonstrated greater therapeutic outcomes and/or expedited therapeutic gains when augmented with DCS relative to placebo across a variety of psychiatric disorders (e.g., anxiety disorders, obsessive-compulsive disorder, post traumatic stress disorder, schizophrenia; Gottlieb et al., 2011; McGuire, Lewin, & Storch, 2014a). Moreover, across multiple RCTs of DCS-augmented treatment, few side effects have been reported with no serious adverse events identified (Ori et al. 2015). Although the results from these RCTs have been mixed across disorders (McGuire et al. 2014a), they bear considerable promise. Indeed, DCS-augmentation of HRT may yield greater overall reductions in tic severity and/or expedited therapeutic gains resulting from enhanced extinction and associative learning.

5. Study Aims

Primary Aim#1: To examine whether a single session of HRT+DCS will produce faster reductions in tic severity relative to HRT+placebo for tics targeted in treatment.

Hypothesis#1: We hypothesize that HRT+DCS will produce faster reductions in tic severity relative to HRT+placebo for tics targeted in treatment on the Hopkins Motor/Vocal Tic Scale (HM/VTS).

6. Administrative Organization

This study will only take place at the University of California Los Angeles (UCLA). There are no other participating study sites, laboratories, data management centers, and/or coordinating centers.

7. Study Design

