This is a double-blind placebo controlled study that will compare the efficacy of a single session of HRT augmented by either DCS or placebo in youth (age 8-17) who have either Tourette Disorder or a Persistent Tic Disorder. The sample size was determined based on the feasibility of the recruitment period. Participants will complete an initial evaluation to determine eligibility (Visit 1). Afterward, eligible youth will be randomly assigned to receive either DCS or placebo prior to a single session of HRT (Visit 2). During this visit, two tics will be targeted for treatment using HRT. One week after the therapy session, youth will return (Visit 3) to complete a follow-up assessment to determine improvement in tics targeted in treatment. The primary outcome measure will be the improvement in two bothersome on the Hopkins Motor/Vocal Tic scale (HM/VTS) at Visit 3.

8. Study Procedures:

Participants:

Included in this study will be up to 20 children and adolescents between the ages of 8 and 17

years (inclusive), who meet diagnostic criteria for Tourette Disorder or a Persistent Tic Disorder and the inclusion and exclusion criteria.

Recruitment:

Recruitment will occur through the UCLA OCD, Anxiety, and Tic Disorder's Program, as well as the greater Los Angeles Community.

Inclusion/Exclusion Criteria:

Inclusion criteria for this study are as follows: (1) ages 8 years to 17 years (inclusive); (2) meet diagnostic criteria for either Tourette Disorder or a Persistent Tic Disorder; (3) moderate tic severity or greater as evidenced by a Yale Global Tic Severity Scale (Leckman, Riddle, Hardin, & Ort, 1989) total score greater than 13 (>9 for children with motor or vocal tics only); (4) be fluent in English; (5) be medication free or on a stable dose of a non-antipsychotic medication for 6 weeks with no planned changes. Co-occurring psychiatric disorders are permissible for enrollment.

Exclusion criteria for this study are as follows: (1) pregnant or breast feeding; (2) an unstable medical condition (e.g., a seizure disorder, kidney or liver disease); (3) current diagnosis of substance abuse/dependence; (4) lifetime diagnosis of schizophrenia, autism spectrum disorder, bipolar disorder, or psychosis; (5) evidence of a seizure disorder, kidney or liver disease, pregnant and/or breast feeding; (6) four or more previous sessions of HRT; or (7) currently taking an antipsychotic medication.

Procedures:

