demographic questionnaire, a parent-report of the child's tic severity called the Parent Tic Questionnaire (PTQ), and a rating scale of ADHD severity called the Swanson Nolan and Pelham Scale-4th edition (SNAP-IV). After completing the video observation protocol, children will be asked to complete a child-report of tic severity called the Child Tic Questionnaire (CTQ), a self-report Premonitory Urge for Tics Scale (PUTS) to measure the child's global premonitory urge, and a self-reported rating scale of puberty development called the Peterson Puberty Development Scale (PDS). For female participants who have had first menses, a pregnancy screen will be conducted. Interested participants who meet full eligibility criteria will be invited back to complete Visit 2 (HRT session) approximately 1 week later.

At Visit 2, participants will arrive and will be randomly assigned to receive either a 50 mg placebo pill or a 50 mg d-cycloserine pill. Evaluating clinicians, participants, and the therapist will be blind to randomization assignment, with only the study coordinator and research pharmacy having access to randomization assignment. As d-cycloserine typically takes 1 hour to become active in participants' system, children and adult will be re-administered the following rating scales to evaluate the current severity of the participant's tics, most bothersome tics, and premonitory urge: the CTQ; PTQ, HM/VTS and I-PUTS. Children will then be asked to complete a computer task to evaluate habit learning called the Weather Prediction task. Afterwards, children will complete a session of HRT that will target two tics in treatment as identified by the HM/VTS. After the participant has completed the session of HRT, the participant will be asked to practice the skills learned in the session over the next week and to document practices using a homework monitoring form. The therapist will complete a session summary sheet to evaluate the patient's mastery of the skills within session. After the completion of the HRT session, a standard side effect form will also be administered to the participant to assess for any side effects. Participants will be asked to return 1 week later for a follow-up assessment. Visit 2 may take up to 4 hours to complete.

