For the purposes of this study, an adverse event is any untoward medical occurrence associated with the use of a drug in humans, whether or not considered drug related.

For the purposes of this study, a serious adverse event is characterized as any adverse drug event (experience) occurring at any dose that in the opinion of the study investigator results in any of the following outcomes: (1) death, (2) life-threatening adverse drug experience, (3) inpatient hospitalization or prolongation of existing hospitalization (for > 24 hours), (4) persistent or significant incapacity or substantial disruption of the ability to conduct normal life functions, (5) congenital anomaly/birth defect, and (6) important medical event (IME) that may jeopardize the subject and may require medical or surgical intervention to prevent one of the outcomes listed in this definition.

Procedures will be used to monitor subject safety

Adverse events will be systematically assessed at Visits 2 and 3 using a standardized adverse event review form (i.e., modified version of the Safety Monitoring Uniform Report Form). This will allow study investigators to monitor for any possible adverse events or side effects from the single administration of d-cycloserine or placebo.

Who (list names) will identify, document, and report adverse events?

The study PI will identify and document adverse events when they have been identified during the study.

What is the frequency for review of summarized safety information and who will perform the review?

Any serious, unanticipated problems (e.g., serious adverse events) will be reported to the IRB within 3 working days of study investigators' awareness.

What are the stopping rules with regard to efficacy and safety?

In the event of a serious adverse event, the subject will discontinue study participation and the attending psychiatrist (the prescribing physician) will be notified. The research staff will monitor the participant closely until the adverse reaction remits.

10. Potential Risks of Study Participation

The risks of participating in this project include relatively lengthy psychiatric evaluations, participating in a single session of HRT, and the medication (placebo or DCS).

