Finally, the potential side effects associated with the administration of DCS include drowsiness, headache, prolonged or momentary dizziness, seizures, confusion, hallucinations, weakness, coma, rash, vitamin B₁₂ deficiency and/or folate deficiency (both of which may cause weakness and anemia), liver enzymes increases (which could cause weakness or bleeding), and shaking. However, these side effects are most commonly related with doses greater than 500mg/day and when dosed chronically (versus acutely), which is at least ten times greater than what we propose to administer in this study. DCS has been approved by the Food and Drug Administration for the treatment of tuberculosis for over 20 years, and, as discussed by Rothbaum et al. 2008, single-pill administrations have been associated with no adverse effects. Furthermore, a recent meta-analysis of over 20 randomized controlled trials of DCS-augmentation that included multiple doses of DCS within each trial, identified no greater adverse event profile relative to placebo with as many as 8 trials reporting no adverse events at all. In the event of a moderate or severe adverse event related to the medication, the subject will be withdrawn from the study, the attending psychiatrist ([name] will be notified), and the research staff will monitor the participant closely until the adverse reaction remits.

Although not a risk directly associated with d-cycloserine, there is always the chance that a participant may report either the perceived risk of suicidality or suicidality itself. In these cases, standard protocol will be followed. If, during an assessment, research staff determines that a

youth endorses a serious mental health program such as suicidal behavior, referral information and telephone numbers to appropriate community services will be provided. The PI will conduct a risk assessment for suicidal ideation and/or behavior. Although unanticipated, if the detected problem is imminent and of crisis status, the PI will take appropriate immediate action including calling emergency services and/or calling UCLA campus police to escort the youth to the emergency department (on-site at UCLA). These situations will be reviewed immediately with the PI's research mentor ([name]), who is a licensed clinical psychologist.

11. Analysis Plan

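### The adverse-event rules withdraw a child from the study, not only from treatment, and make no provision for Visit 3, so a child withdrawn before the Visit 3 rating has no primary outcome

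*Combined protocol and SAP*

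**What the plan says.** Two sections of the protocol set out what happens to a child after an adverse event.

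- Section 10 (Potential Risks of Study Participation): "In the event of a moderate or severe adverse event related to the medication, the subject will be withdrawn from the study".
- Section 9 (Safety Monitoring Plan), under stopping rules: "In the event of a serious adverse event, the subject will discontinue study participation".

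Both then provide for telling the attending psychiatrist and for close monitoring until the reaction resolves. Neither mentions Visit 3, and nowhere do the documents separate stopping treatment from stopping assessment.

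The timing comes from sections 7 to 9. The pill is given at Visit 2, and the HM/VTS is repeated while it takes effect. Then: "Afterwards, children will complete a session of HRT that will target two tics in treatment as identified by the HM/VTS". The first safety check follows: "After the completion of the HRT session, a standard side effect form will also be administered to the participant". A week of home practice leads to Visit 3, where the HM/VTS and a second side effect form are completed. Section 9 confirms the safety schedule: "Adverse events will be systematically assessed at Visits 2 and 3 using a standardized adverse event review form". Section 7 defines the endpoint: "The primary outcome measure will be the improvement in two bothersome on the Hopkins Motor/Vocal Tic scale (HM/VTS) at Visit 3".

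Section 11 enters the average of the two targeted tics over three visits into a repeated measures ANOVA. It names neither an analysis population nor a method for missing data.

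**The concern.** In a trial with repeated dosing, withdrawal may protect a child from further exposure. Here, once the HRT session is over, no pill or session remains. Ending participation then removes home practice as a study activity, the only HM/VTS rating made after HRT, and the second standardised side effect form. Both earlier HM/VTS ratings precede HRT and cannot stand in for the outcome.

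An outcome lost in this way is removed by a stated rule because of something that happened after randomisation. The comparison would no longer cover every child randomised, in a trial of at most 20. The child who had a notable reaction would also be the one without the standardised one-week safety assessment.

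**Working it through.** The plan gives no event rate, dropout allowance, power or standard deviation, so it has no figure to reproduce. The check is first textual, then a small illustration.

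**When the outcome is lost**

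| Event identified and acted on | HM/VTS after HRT | Visit 3 side effect form |
|---|---|---|
| After the pill, before HRT | Lost; the HRT session would also be at issue | Lost |
| At the Visit 2 form, after HRT | Lost | Lost |
| Reported between Visits 2 and 3 | Lost | Lost |
| At Visit 3, after the HM/VTS rating | Kept | Depends on the stage of the visit |

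Section 8 mentions the HM/VTS before the side effect form at Visit 3, but does not fix the order. The loss therefore depends on the event being acted on before that rating.

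**Size of one loss**

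Inputs: up to 20 children (section 8); each tic scored 0 to 4 (section 8), so a two-tic average also runs from 0 to 4. Assumptions: 10 per arm, since no allocation ratio is stated, and a common SD of 1.

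1. Standard error (SE) of the arm difference, no loss: √(1/10 + 1/10) = √0.2 = 0.447 SD.
2. One loss: √(1/10 + 1/9) = 0.459 SD. Ratio: 0.459/0.447 = 1.027, a rise of 2.7%.
3. Range of the arm mean that the missing score leaves open: (4 − 0)/10 = 0.4 points.
4. If the lost child differs from the other nine by g SD, the arm mean shifts by g/10. For assumed g of 0.5 to 1.0 this is 0.05 to 0.10 SD, or 0.05/0.447 = 11% to 0.10/0.447 = 22% of the SE.

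**How many losses**

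With an assumed chance p per child of a qualifying event acted on before the Visit 3 rating, the expected number lost is 20p and the chance of at least one is 1 − (1 − p)^20.

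| Assumed p | Expected losses | Chance of at least one |
|---|---|---|
| 0% | 0 | 0% |
| 1% | 0.2 | 18% |
| 2% | 0.4 | 33% |
| 5% | 1.0 | 64% |

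**Whether analysis can replace the missing score**

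For the Visit 2 to Visit 3 change with correlation r, dropping the child gives an arm variance of 2(1 − r)/9. A likelihood-based model that keeps the child's Visit 2 score gives (1 − r²)/9 + (1 − r)²/10. With no loss it is 2(1 − r)/10.

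- At r = 0.5: (0.1083 + 0.1)/0.2 = 1.0417, square root 1.021.
- At r = 0.7: (0.0657 + 0.06)/0.12 = 1.0472, square root 1.023.

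The rise in SE falls only from 2.7% to 2.1% or 2.3%. This uses two visits and assumes that the score is missing at random. Only the Visit 3 rating itself restores the information.

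**The case against.** The strongest objection is that the rule may never be used. Section 10 says that "single-pill administrations have been associated with no adverse effects", and section 4 says of earlier trials that "few side effects have been reported with no serious adverse events identified". Section 10 adds that pooled trials showed no worse adverse event profile than placebo. Participants, evaluating clinicians and the therapist are blinded. This stands: the expected loss may be zero. It does not make the risk nil, since section 4 speaks of few side effects rather than none, and the sponsor saw fit to write a withdrawal rule.

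Second, many serious events under section 9 would make Visit 3 impossible whatever the rule said. This also stands. The avoidable loss comes mainly from the section 10 rule.

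Third, full withdrawal may be deliberate: section 10 stresses limiting burden, and Visit 3 can take 2 hours. Consent pages are not in the reviewed copy, so any wording there on data after withdrawal cannot be seen. A retained score might also follow a week of interrupted practice, which affects what it means. These are reasons to state the intention clearly and to record interruptions, not to leave the matter silent.

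A reader might infer more than the documents support:

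- That the comparison will be biased towards or against DCS. No rate or direction is given, and the safety statements above weaken any expectation of unequal loss.
- That safety follow-up is abandoned. Both rules keep monitoring until the reaction resolves; what is lost is the standardised Visit 3 form.
- That the two triggers contradict each other, or that one is plainly the broader. Section 10 turns on severity and relation to the medication, section 9 on seriousness. Section 9 defines an adverse event regardless of relation to the drug, yet frames a serious one as an adverse drug event. The text does not settle how far they overlap.
- That the planned ANOVA would certainly drop such a child. This is likely for a classical analysis but is not stated.

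**Conclusion.** The concern holds in a limited form. Followed as written, the rules would remove a randomised child's primary outcome and Visit 3 side effect form if a qualifying event is acted on before the Visit 3 rating, while preventing no further dosing once the HRT session is over.

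The effect on precision is small: 2.7% on the SE per child lost, assuming 10 per arm. The larger issue is an outcome removed because of a post-randomisation event, which leaves up to 0.4 points of an arm mean undetermined on a 0–4 scale. Every event rate used here is an assumption, the number lost may be zero, and the direction of any effect is unknown. The change is still worth making, because the loss would come from a stated rule and the assessment that avoids it is already scheduled. Confidence is medium.

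**What to change.** State in sections 9 and 10 that meeting a withdrawal criterion does not by itself end outcome collection. The scheduled Visit 3 HM/VTS and adverse event form are still sought if the family agrees and the child's condition allows. Add to section 11 that these children are analysed in their assigned arm, and that withdrawals and any interruption of home practice are reported by arm.

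The sponsor should also reconcile the differing withdrawal triggers in sections 9 and 10. No view is taken here on which is right, or on when treatment should stop.

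The cost is one or two sentences in sections 9 and 10 and a short addition to section 11, with no new visit. Some families may decline, Visit 3 takes up to 2 hours, and a retained score may follow interrupted practice. A mixed model, or a best/worst-value sensitivity analysis if a Visit 3 score is missing, is optional; neither replaces collecting the score.

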At Visit 3, participants will complete a battery of tic assessment to monitor change in tic severity. These assessments will be administered by a clinician blind to randomization assignment, and will include the YGTSS, I-PUTS, HM/VTS, and the Clinical Global Impression of Improvement that serves as a global rating of improvement of tics. Participants will also be administered a standard side effect form to monitor for any possible side effects of d-cycloserine. Children will complete a standardized 10 minute video observational protocol to identify the frequency and severity of tics (Himle et al. 2006). Parents will be asked to complete the PTQ to assess parent report of tic severity and a homework compliance monitoring form to evaluate the participant's practice of skills learned in HRT over the past week. Children will be asked to complete the CTQ to assess child-reported tic severity and the PUTS to evaluate their premonitory urge globally. Children will also complete a homework compliance form. This visit may take up to 2 hours. Participants and their families will be collectively compensated \$30 for each study visit.

Tests/Measures Administered:

The following measures and tasks will be administered this study.

Clinician Administered:

Anxiety Disorder Interview Schedule-Parent and Child Version (ADIS-C/P; Silverman & Albano, 1996). This is a clinician-administered, structured diagnostic interview based on DSM-IV diagnostic criteria. Diagnoses reflect endorsement of symptoms as well as a severity rating (patient impairment/distress) of at least 4 on a 0-8 scale. The tic disorder section, created

by [name], will be used to confirm tic diagnoses. The ADIS-C/P is widely used in both research and practice.

Yale Global Tic Severity Scale (YGTSS; Leckman et al., 1989). The YGTSS is a semi-structured interview that examines the presence and severity of motor and phonic tics over the previous week across 5 domains: total motor tics, total phonic tics, total tics, overall impairment rating, and a global severity score. The YGTSS has well-supported psychometric properties (Storch et al., 2005; Leckman et al., 1989).

Individualized Premonitory Urge for Tics Scale (I-PUTS). The I-PUTS is a clinician-administered scale that assess the frequency, intensity and body region of premonitory urges that are associated with tics endorsed on the YGTSS.

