Descriptive statistics will be used to characterize the entire sample and two conditions (DCS, placebo). Independent sample t-tests and chi-square tests will be used to examine for between-group differences (DCS versus placebo) for continuous and categorical variables respectively. Although no significant differences in conditions are expected due to random assignment, any significant between group differences will be controlled for during data analysis. Given that co-occurring ADHD and alpha-2 agonists have been found to influence tic severity outcomes to HRT, these will interested a covariates at baseline.

The primary outcome in this study will be the reduction in bothersome tic severity on the HM/VTS for the two tics targeted in treatment. The average score for these two bothersome tics will be interested into a repeated measures analysis of variance (ANOVA), with the covariates of ADHD diagnosis and alpha-2 agonist status at baseline. The diagnosis of ADHD will be identified from the structured clinical interview (ADIS), and alpha-2 agnostic will come from demographic information form. This data will be entered across three assessment visits, with a between group factor of treatment condition (DCS+HRT or PLBO+HRT).

References

Achenbach, T. M., & Rescorla, L. A. (2001). *Manual for the ASEBA School-Age Forms & Profiles*. Burlington, VT: University of Vermon, Research Center for Children, Youth & Families.

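### Section 11 picks extra covariates by significance-testing the randomised arms, so they are chosen by chance imbalance and not by prognostic value; fixing them in advance is a cheap improvement

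*Combined protocol and SAP*

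**What the plan says.** In the combined protocol and SAP, the first paragraph of section 11 sets out the screen: "Independent sample t-tests and chi-square tests will be used to examine for between-group differences (DCS versus placebo"), on continuous and categorical variables that it does not name. The authors expect no significant differences because of randomisation, but add that "any significant between group differences will be controlled for during data analysis". They give no significance level, no cap on the number of added covariates, and no requirement that an added variable be related to outcome.

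The same section fixes two covariates for a stated prognostic reason: ADHD and alpha-2 agonists are said to influence tic outcome after HRT. The primary analysis is a repeated measures ANOVA of the mean HM/VTS score for the two treated tics, "with the covariates of ADHD diagnosis and alpha-2 agonist status at baseline". On the design of that model it says: "This data will be entered across three assessment visits, with a between group factor of treatment condition (DCS+HRT or PLBO+HRT"). Flagged variables are not mentioned there, nor is it said whether covariates enter as main effects only or also interact with visit.

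On size, section 8 (Participants) says: "Included in this study will be up to 20 children and adolescents".

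**The concern.** Randomisation makes any baseline difference between arms a matter of chance. A significance test of such a difference therefore says nothing useful about whether the variable should be adjusted for. What matters is how strongly the variable predicts HM/VTS, and the rule does not ask that. A prognostic variable 0.8 SD out of balance is ignored, while an irrelevant one at 0.95 SD is adjusted for.

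At stake is precision in a small trial. An irrelevant covariate that is strongly imbalanced is, by construction, correlated with treatment arm, so adjusting for it widens the standard error of an adjusted between-group contrast and uses a residual degree of freedom. A second issue is reproducibility: the primary model cannot be written down before the data are seen, and two analysts could fit different models while both following the plan.

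**Working it through.** **Inputs.** From the documents: N up to 20, two named covariates, three visits. The plan gives no allocation ratio, significance level or candidate list, and N was set by feasibility, so there is no power figure to reproduce. Assumed: 10 per arm, two-sided 0.05, ADHD in 50%, alpha-2 agonist use in 30%, and 5, 10 or 20 candidate variables. That range is realistic: section 8 lists seven demographic items and about ten Visit 1 measures (YGTSS, I-PUTS, HM/VTS, CGI-S, video count, PTQ, SNAP-IV, CTQ, PUTS, PDS).

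**1. Smallest imbalance flagged.** t(0.975, 18 df) × sqrt(2/10) = 2.101 × 0.447 = 0.940 SD, whatever the variable's prognostic value.

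**2. Chance of at least one flag.** With k independent continuous tests, 1 − 0.95^k = 23%, 40% and 64% for k = 5, 10 and 20. With pairwise correlation 0.5 it is about 18%, 29% and 43%. Categorical candidates are flagged less often (3.0%-4.2% each by uncorrected chi-square at prevalence 20%-50%).

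**3. Cost of one irrelevant flagged covariate.** In a model with arm only, a covariate exactly at the threshold has R² with arm = 2.101²/(2.101² + 18) = 0.197. The variance inflation is 1/(1 − 0.197) = 1.245, and sqrt(1.245) = 1.116, so the standard error rises by 11.6%.

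**4. Cost averaged over trials.** Simulation of a single between-group contrast compared a fixed model (arm, ADHD, alpha-2 agonist) with the same model plus every flagged candidate, for independent non-prognostic candidates and a true effect of 1.25 SD:

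| Candidates | Power, fixed | Power, rule | Mean SE rise |
|---|---|---|---|
| 5 | about 69% | 66% | 4%-5% |
| 10 | about 69% | 63% | 9% |
| 20 | about 69% | 56% | 18% |

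Repeat runs agree to within about one percentage point of power. The loss shrinks if candidates are correlated 0.5 and jointly explain 30% of outcome variance: against about 70% for the fixed model, power under the rule is 70%, 69% and 65%.

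**5. Type I error.** Under the null the rule rejects in about 5% of trials, with mean bias within 0.01 SD. If either the fixed or the rule-based model may be reported, rejection is 5.4%, 6.2% and 6.7% for the between-group contrast with 5, 10 and 20 candidates.

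**6. Treatment-by-visit test.** The simulation assumed visit correlations of 0.7/0.6/0.6 and a 1.0 SD effect at Visit 3. With complete data and main-effect covariates, power is 70%-71% with or without flagged covariates, because between-subject main effects drop out of the within-subject contrasts. With covariate-by-visit terms and non-prognostic candidates, power falls from about 65% to 62%, 58%-60% and 53%. If either model may be reported in that case, null rejection is 5.5%, 5.9% and 7.1%.

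**7. What the rule gains when a flagged variable is prognostic.** Among data sets in which a covariate is flagged, root mean square error (RMSE) of the treatment estimate, fixed v adjusted, is 0.57 v 0.54 SD at covariate-outcome correlation 0.3, and 0.67 v 0.50 SD at 0.5. Null rejection given a flag at correlation 0.5 is 16% v 5%. The reason is direct: an imbalance of 0.94 SD times a slope of 0.5 shifts the unadjusted estimate by 0.94 × 0.5 = 0.47 SD. Adjusting gives the smaller error once the correlation exceeds about 0.25-0.3.

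**The case against.** The strongest defence is step 7. When a moderately prognostic variable happens to be badly imbalanced, adjusting brings that trial's estimate closer to the truth, and the correlation needed is modest. Comparing reported standard errors alone would put break-even near 0.6, but that ignores the shift in the unadjusted estimate. This objection stands as a real cost of the fix. It does not rescue the rule, which cannot tell such a variable from an irrelevant one, and the fixed model remains valid averaged over randomisations.

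It is also fair that the aim concerns faster reduction in tic severity over three visits. Treatment-by-visit is then the natural test, and step 6 shows no loss there with main-effect covariates. The between-group figures matter only if that contrast is used. The plan does not name the test or the form of the covariates.

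A reader might infer that the plan would adjust for variables measured after treatment, and so bias the estimate. Section 8 says "At Visit 2, participants will arrive and will be randomly assigned", then that "children and adult will be re-administered the following rating scales", and at Visit 3 parents complete "a homework compliance monitoring form to evaluate" practice. Nothing expressly excludes these measures. But the trigger sentence rests on randomisation making differences unexpected, which fits only variables that treatment cannot affect. Visit 2 HM/VTS is moreover part of the outcome. Baseline variables are clearly meant; stating this is a minor clarification.

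Finally, section 11 describes only one inferential outcome analysis, so flagged variables most naturally enter that model. The freedom to choose models is real but narrow.

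**Conclusion.** The point holds as a cheap improvement. The rule selects covariates on the wrong criterion and leaves the covariate set dependent on the data, with N up to 20. Its main harm is lost precision in a between-group contrast: about 3, 6 and 13 points of power (69% less 66%, 63% and 56%) with 5, 10 and 20 independent non-prognostic candidates, and less if candidates are correlated and prognostic. These are scenarios, not bounds; allocation, alpha, candidate number, prevalences and effect size are all assumed.

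Two stronger conclusions are not supported. The rule does not itself inflate type I error: applied mechanically to baseline variables it stays near 5% and is unbiased on average, and the mild inflation to about 5.5%-7% needs an analyst who chooses between models. Nor is the primary test necessarily weakened: treatment-by-visit is untouched with complete data and main-effect covariates, and loses power only with covariate-by-visit terms.

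**What to change.** - Delete the between-group significance tests and the sentence that triggers adjustment. Describe baseline characteristics by arm instead.
- State that the primary model's covariates are ADHD diagnosis and alpha-2 agonist status only, which section 11 already justifies on prognostic grounds. A phrase saying whether they enter as main effects or also with visit terms would settle step 6.
- Label any further adjustment as a sensitivity analysis limited to variables measured at Visit 1.

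This takes a few sentences and needs no new data or participants. The downside is that if a covariate correlated with outcome above about 0.25-0.3 turns out badly imbalanced, the primary estimate in that trial will tend to lie further from the truth than the adjusted one (RMSE about 0.67 v 0.50 SD at correlation 0.5), and the adjusted result will appear only in the sensitivity analysis.
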